3.2 Discussion and Rationale for Study Design

3.2.1 Study Design

This is a single-arm, open-label study in third-line and later SCLC. Rovalpituzumab tesirine has previously demonstrated preliminarily promising efficacy and tolerability in both second- and third-line SCLC. Because there is no approved therapy for third-line SCLC, no appropriate active comparator is available. At the same time, the very poor prognosis of subjects in this setting makes placebo comparison inappropriate.

3.2.2 Dose Rationale

The chosen dose regimen, two doses of 0.3 mg/kg administered 6 weeks apart, is based on the safety and efficacy observed in a previous phase 1 study (SCRX16-001), where delayed and/or cumulative toxicities were observed with both q3wk and q6wk schedules and appeared to be related to total dose administered. The total dose was therefore capped at a total cumulative dose of 0.6 mg/kg and the finite dosing regimens of 0.2 mg/kg q3wk for a total of 3 doses (q3wk x 3) and 0.3 mg/kg q6wk for a total of 2 doses (q6wk x 2) were evaluated in expansion cohorts.

Because the intended mechanism of action of rovalpituzumab tesirine is to target cancer stem

cells and, more broadly, tumor-initiating cells, limiting the number of doses is hypothesized to affect anti-tumor response only minimally.

The 0.2 mg/kg q3wk x 3 and 0.3 mg/kg q6wk x 2 dosing regimens demonstrated comparable objective response and clinical benefit rates. Both regimens were tolerated, but the 0.3 mg/kg regimen demonstrated a trend towards lower rates of treatment-emergent adverse events (TEAE), related TEAEs, Grade 3/4 TEAEs and related Grade 3/4 TEAEs. In addition, although the 0.3 mg/kg regimen appeared to have a higher incidence of Grade 3/4 thrombocytopenia, such an AE was generally clinically manageable.

██████████ serosal effusions, which may be life threatening such as leading to pericardial tamponade. In addition, objectives responses preliminarily have appeared to be more durable in subjects treated with the 0.3 mg/kg regimen. Finally, the 0.3 mg/kg q6wk x 2 regimen is more conveniently administered than 0.2 mg/kg q3w x 3 and coincides with the timing of radiographic evaluation of tumor size. Therefore, 0.3 mg/kg q6wk x 2 is the chosen dose regimen for this study.

3.2.3 Blinding

This is not a blinded trial. However, sponsor-independent review of efficacy and safety will occur throughout the study (Sections [7.2.1](#) and [0](#)).

4 STUDY POPULATION

Subjects must meet all of the enrollment criteria to be eligible for this study. Eligibility criteria may not be waived by the investigator and are subject to review in the event of Good Clinical Practice (GCP) audit and/or appropriate health regulatory authority inspection.

To be eligible for retreatment as described in Section 3.1, subjects must meet all inclusion and exclusion criteria outlined in this section.

4.1 Inclusion Criteria

1. Adult aged 18 years or older
2. Histologically confirmed small-cell lung cancer (SCLC) with documented disease progression after at least 2 prior systemic regimens, including at least one platinum-based regimen
3. DLL3-expressing SCLC based on central immunohistochemistry (IHC) assessment of banked or otherwise representative tumor tissue.
4. Measurable disease, defined as at least 1 tumor lesion ≥ 10 mm in the longest diameter or a lymph node ≥ 15 mm in short-axis measurement assessed by CT scan (RECIST v1.1)
5. Eastern Cooperative Oncology Group (ECOG) performance status of 0 or 1. See Appendix 12.2 for conversion of performance status using Karnofsky scales, if applicable
6. Minimum life expectancy of at least 12 weeks
7. Subjects with a history of central nervous system (CNS) metastases must have documentation of stable or improved status based on brain imaging for at least 2 weeks after completion of definitive treatment and within 2 weeks prior to first dose of Study Drug, off or on a stable dose of corticosteroids. Definitive treatment may include surgical resection, whole brain irradiation, and/or stereotactic radiation therapy
8. Recovery to Grade 1 of any clinically significant toxicity (excluding alopecia) prior to initiation of study drug administration
9. Satisfactory laboratory parameters:
 - a. Absolute neutrophil count (ANC) $\geq 1,500/\mu\text{L}$
 - b. Platelet count $\geq 75,000/\mu\text{L}$

- c. Hemoglobin \geq 8.0 g/dL
- d. Serum total bilirubin \leq 1.5x upper limit of normal (ULN) or \leq 3x ULN for subjects with Gilbert's disease
- e. Serum alanine aminotransferase (ALT) and aspartate aminotransferase (AST) \leq 2.5x ULN (\leq 5x ULN if evidence of hepatic involvement by malignant disease)
- f. Serum creatinine \leq 1.5x ULN or estimated glomerular filtration rate (eGFR) \geq 30 mL/min/1.73 m² as calculated by the 4-variable Modification of Diet in Renal Disease (MDRD) study equation (GFR (mL/min/1.73 m²) = 175 \times (serum creatinine [mg/dL]) $-1.154 \times$ (age [years]) -0.203×0.742 (if female) $\times 1.212$ (if African American; [Levey, 2006](#))

10. Last dose of any prior therapy administered by the following time intervals before the first dose of study drug:

- a. Chemotherapy, small molecule inhibitors, radiation, and/or other investigational anticancer agents (excluding investigational monoclonal antibodies): 2 weeks
- b. Immune-checkpoint inhibitors (i.e., anti-PD-1, anti-PD-L1, or anti-CTLA-4): 4 weeks
- c. Other monoclonal antibodies, antibody-drug conjugates, radioimmunoconjugates, or T-cell or other cell-based therapies: 4 weeks (2 weeks with documented disease progression)

11. Females of childbearing potential must have a negative beta human chorionic gonadotropin (β -hCG) pregnancy test result within 7 days prior to the first dose of study drug. Females of non-childbearing potential are those who are postmenopausal greater than 1 year or who have had a bilateral tubal ligation or hysterectomy.

- a. Females of childbearing potential and males who have partners of childbearing potential must agree to use an effective contraception method during the study and for 1 year following the last dose of study drug. Effective birth control includes (a) combined, estrogen and progestogen containing, hormonal contraception (oral, intravaginal, transdermal); (b) progestogen-only hormonal contraception (oral, injectable, implantable); (c) intrauterine device (d) intrauterine hormone-releasing system; (e) bilateral tubal occlusion; (f) vasectomised partner; and (g) sexual abstinence.

4.2 Exclusion Criteria

1. Any significant medical condition, including any suggested by screening laboratory findings that, in the opinion of the investigator or sponsor, may place the subject at undue risk from the study, including but not necessarily limited to uncontrolled hypertension and/or diabetes, clinically significant pulmonary disease (e.g., chronic obstructive pulmonary disease requiring hospitalization within 6 months) or neurological disorder (e.g., seizure disorder active within 6 months)
2. Documented history of a cerebral vascular event (stroke or transient ischemic attack), unstable angina, myocardial infarction, or cardiac symptoms consistent with New York Heart Association (NYHA) Class III–IV (see Appendix 12.3) within 6 months prior to their first dose of study drug
3. Recent or ongoing serious infection, including:
 - a. Any active grade 3 or higher (per NCI CTCAE version 4.03) viral, bacterial, or fungal infection within 2 weeks of the first dose of the study drug. Routine antimicrobial prophylaxis is permitted.
 - b. Known seropositivity for or active infection by human immunodeficiency virus (HIV)
 - c. Active Hepatitis B (by surface antigen expression or polymerase chain reaction) or Hepatitis C (by polymerase chain reaction) infection or on hepatitis-related antiviral therapy within 6 months of first dose of study drug.
4. Women who are breastfeeding
5. Systemic therapy with corticosteroids at >20 mg/day prednisone or equivalent within 1 week prior to the first dose of study drug
6. History of another invasive malignancy that has not been in remission for at least 3 years. Exceptions to the 3 year limit include nonmelanoma skin cancer, curatively treated localized prostate cancer, and cervical cancer *in situ* on biopsy or squamous intraepithelial lesion on PAP smear
7. Prior exposure to a pyrrolobenzodiazepine (PBD)-based drug, or known hypersensitivity to rovalpituzumab tesirine or excipient contained in the drug formulation, unless undergoing retreatment with rovalpituzumab tesirine in the context of this protocol

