Retreatment with rovalpituzumab tesirine is permitted for subjects who tolerate two doses of rovalpituzumab tesirine, achieve clinical benefit as defined by stable disease or better, have received no other systemic anti-cancer therapy after rovalpituzumab tesirine as administered in this protocol, and with central radiographic assessment-confirmed disease progression at least 12 weeks after the second dose. Retreatment consists of rovalpituzumab tesirine 0.3 mg/kg IV once every 6 weeks for two cycles, or a reduced dose if dose reduction has previously taken place (see Section 5.2.3.2). Additional retreatment, beyond a total of four cycles will require approval from the Medical Monitor.

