5.2.3.2 Dose Reduction Guidelines

Rovalpituzumab tesirine dose reduction for specific toxicities should occur as outlined in Table 5-1 and Table 5-2. If toxicities persist despite dose reduction, the dose should be discontinued. Exceptions to the dose modification guidelines may be permitted with written or electronic approval from the Medical Monitor. If a dose is reduced during the previous cycle, the reduced dose will be administered on Day 1 of subsequent cycles.

Table 5-1 Dose Reductions for Rovalpituzumab Tesirine

Starting Dose	First Dose Reduction (reduce dose)	Second Dose Reduction (discontinue dose)
0.3 mg/kg	0.2 mg/kg	Discontinue dosing

Table 5-2 Unacceptable Toxicities Requiring Dose Reduction

Toxicity	Grade ^a / Details
Thrombocytopenia	Grade 4 thrombocytopenia (or Grade 3 thrombocytopenia with bleeding) lasting more than 7 days and/or requiring platelet transfusion
Thrombocytopenia with bleeding	
Neutropenia	Grade 4 neutropenia lasting more than 7 days and/or requiring hematopoietic growth factor rescue, or any febrile neutropenia (Grade 3 or 4 neutropenia with concurrent fever $\geq 38.3^{\circ}\text{C}$)
Febrile neutropenia	
Laboratory abnormality	Grade 2 or higher hypoalbuminemia (in subject with normal baseline albumin levels) Grade 3 or 4 non-albumin laboratory abnormality considered clinically significant and treatment-related
Nonlaboratory toxicity	Grade 3 or 4 nonlaboratory toxicity (including infusion reactions) with the exception of fatigue, asthenia, nausea, or other manageable constitutional symptom
Skin toxicity	Grade 3 or higher cutaneous toxicity or symptom of photosensitivity (refer to Section 5.5.2)
Serosal effusions	Serosal effusions including: Grade 3 or higher pericardial effusion Grade 2 or higher pleural effusion Grade 3 or higher peripheral edema

a) Refer to Appendix 12.5 for definitions of NCI-CTCAE severity grades.

For the purposes of dose reduction, unacceptable toxicity is defined in Table 5-2. If unacceptable toxicity is encountered in Cycle 1, the Cycle 2 dose may be reduced (Table 5-1). If unacceptable toxicity is encountered at the reduced dose level, treatment should be discontinued. If the rovalpituzumab tesirine dose is reduced, the reduced dose level will be used for any subsequent cycles (i.e., retreatment).

Treatment guidelines for hematologic toxicities, and recommended actions regarding rovalpituzumab tesirine dosing, are outlined in Table 5-3.

Table 5-3 Guidelines for Hematologic Toxicities

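### Exclusion criterion 7 waives the known-hypersensitivity bar for retreatment, although only the prior-PBD bar needs waiving

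*Protocol*

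**What the plan says.** Criterion 7 in Protocol Section 4.2 joins two conditions and closes with one exemption. It excludes prior exposure to a PBD-based drug "or known hypersensitivity to rovalpituzumab tesirine or excipient contained in the drug formulation, unless undergoing retreatment with rovalpituzumab tesirine" under this protocol.

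Section 4 makes the same list the eligibility test for retreatment: "To be eligible for retreatment as described in Section 3.1, subjects must meet all inclusion and exclusion criteria outlined in this section". It also says that the investigator may not waive criteria. Section 6.2 keeps the eligibility review in the retreatment screening visit.

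Other provisions bear on a subject who reacted to the drug in the first course:

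- Section 3.1: "Retreatment with rovalpituzumab tesirine is permitted for subjects who tolerate two doses of rovalpituzumab tesirine", subject to further conditions, including centrally confirmed progression at least 12 weeks after the second dose.
- Section 4.1, criterion 8: "Recovery to Grade 1 of any clinically significant toxicity (excluding alopecia) prior to initiation of study drug administration".
- Section 4.2, criterion 1 excludes a significant medical condition that, "in the opinion of the investigator or sponsor, may place the subject at undue risk from the study".
- Table 5-2 in Section 5.2.3.2 lists, among toxicities calling for dose reduction, "Grade 3 or 4 nonlaboratory toxicity (including infusion reactions" and others). The same section adds: "If the rovalpituzumab tesirine dose is reduced, the reduced dose level will be used for any subsequent cycles (i.e., retreatment").

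The synopsis gives the eligibility rule in short form. It attaches the retreatment exemption to PBD exposure and does not mention hypersensitivity.

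**The concern.** The two conditions in criterion 7 do different work at retreatment. Without an exemption, the exposure condition would exclude every candidate, because the study drug is itself PBD-based. The hypersensitivity condition would exclude only those known to be hypersensitive, which is its purpose, so it needs no exemption.

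As punctuated, the exemption covers both. The hypersensitivity exclusion therefore applies at first enrolment, when few subjects could know of a hypersensitivity to this drug, and lapses at retreatment, when some could. Whether such a subject is infused again then depends on an undefined term and on discretion. The issue is patient safety on re-exposure. Retreatment efficacy and safety are exploratory objectives, so no confirmatory result depends on it.

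**Working it through.** The plan gives no figure on this point to reproduce. The check is one of wording, followed by a short scale calculation.

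**Step 1: possible readings of the exemption in criterion 7**

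| Exemption governs | PBD bar at retreatment | Hypersensitivity bar at retreatment | Assessment |
|---|---|---|---|
| Both conditions | waived | waived | Workable, and the natural reading of one clause set off by a comma |
| Nearer condition only | stands | waived | Unworkable: every retreatment candidate would be excluded |
| First condition only | waived | stands | Matches the synopsis, but the word order does not support it |

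The exemption comes after the hypersensitivity condition, so both readings that the word order allows waive that bar. The only workable one waives both.

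**Step 2: whether another rule restores the bar**

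- *Tolerated two doses (Section 3.1).* Not defined, and hypersensitivity is not named.
- *Exclusion 1.* A judgement by investigator or sponsor, with no mandatory trigger for hypersensitivity.
- *Inclusion 8.* Met once a toxicity has recovered to Grade 1. Retreatment follows progression at least 12 weeks after dose 2, by which time an acute reaction would normally have resolved.
- *Table 5-2.* A Grade 3 or 4 infusion reaction leads to dose reduction. Discontinuation follows only if unacceptable toxicity occurs at the reduced dose, and the Medical Monitor may approve exceptions to the dose-modification guidelines.
- *Liver injury (Section 7.6.1.7).* Retreatment after possible drug-induced liver injury with discontinuation needs approval from the sponsor and the medical monitor. The protocol thus contains a toxicity-specific retreatment control, but none for hypersensitivity.

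The protocol does foresee such reactions. Section 5.4.2 allows high-dose corticosteroids to prevent or manage them, and Section 7.6.3 asks for more frequent vital signs when they occur.

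**Step 3: a pathway under the rules as written**

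1. A subject has a Grade 3 infusion reaction in Cycle 1.
2. The Cycle 2 dose is reduced from 0.3 to 0.2 mg/kg (Tables 5-1 and 5-2) and is given without unacceptable toxicity.
3. The subject has stable disease or better, then centrally confirmed progression at least 12 weeks after dose 2.
4. The subject is judged to have tolerated two doses and is considered for retreatment at 0.2 mg/kg.
5. If the Cycle 1 reaction was hypersensitivity, criterion 7 still does not exclude the subject.

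**Step 4: scale**

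Exposure at stake over the two retreatment cycles (Section 3.1, with doses from Table 5-1):

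- reduced dose: 2 × 0.2 = 0.4 mg/kg
- full dose: 2 × 0.3 = 0.6 mg/kg

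The documents give neither a retreatment rate nor a hypersensitivity rate. For illustration only, assume that 10% to 30% of subjects become retreatment candidates and that 1% to 5% of those are hypersensitive. On the planned 123 DLL3 high third-line subjects:

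- low: 123 × 0.10 × 0.01 = 0.123
- high: 123 × 0.30 × 0.05 = 1.845

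That is about 0.1 to 1.8 subjects. Total enrolment is larger, because other DLL3 positive subjects and fourth-line or later subjects can also enter and be retreated, so this base is too small. The conclusion does not rest on the count.

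**The case against.** The strongest reply is that the intent is clear and the practical risk is small. The synopsis shows that the sponsor meant to exempt PBD exposure only. Retreatment conditions are cumulative, so the exemption in criterion 7 does not remove the tolerability requirement in Section 3.1, and Exclusion 1 remains available. The subject in the pathway above has already been re-challenged at 0.2 mg/kg without unacceptable toxicity and would be retreated at that same dose, which is some evidence of tolerance. A first reaction in Cycle 2 is the harder case, and there the tolerability condition bears directly.

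Much of this stands. These safeguards would probably stop most serious cases, and nothing shows that a hypersensitive subject would in fact be re-dosed. But none of them bars known hypersensitivity, and the synopsis is evidence of intent rather than a replacement for Section 4.2, which sites apply. Clear intent is a reason to correct the wording.

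A second reply is that a separate criterion would also rest on judgement, because known hypersensitivity is not defined either. Section 7.6.1.2 tells sites to record each sign or symptom of an infusion-related reaction separately and not to use the allergic or hypersensitivity terms, so the adverse event record may not show a reaction as hypersensitivity. This is a fair limit on what the correction can achieve. It also weakens the tolerability safeguard, since a reviewer may see scattered symptoms instead of one named reaction. With the criterion restored, a reaction that has been judged to be hypersensitivity leads to exclusion; under the present text it does not.

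**Conclusion.** The concern holds: as written, criterion 7 waives the known-hypersensitivity exclusion for retreatment candidates, and no other rule puts it back. This follows from the text alone and needs no assumed rate. The severity is minor. For an affected subject the stake is 0.4 to 0.6 mg/kg over cycles 3 and 4, plus any further cycles that the Medical Monitor approves. The number of such subjects cannot be derived from the documents and is likely to be small. The ORR and OS analyses, the sample size and the error rates are unaffected.

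**What to change.** Split the criterion at the next amendment:

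- *Criterion 7:* previous treatment with any PBD-based agent, except for a subject being retreated under this protocol.
- *Criterion 8:* known hypersensitivity to the study drug or any of its excipients, with no retreatment exception.

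This brings Section 4.2 into line with the synopsis. Infusion reactions that the investigator does not judge to be hypersensitivity stay under Table 5-2, unchanged.

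The cost is a one-sentence change and possibly a few fewer retreated subjects in an exploratory analysis. It also leaves an asymmetry: Table 5-2 could still allow a reduced Cycle 2 dose to a subject whose reaction is judged to be hypersensitivity, while criterion 8 would bar that subject from retreatment. That is acceptable, but the amendment should say it is intended.

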4.3 Removal of Subjects from Therapy or Assessment

The sponsor or its designee must be notified if a subject is withdrawn from study treatment or from the study. The reason(s) for withdrawal must be documented in the subject's medical records and case report form (CRF). When a subject withdraws from treatment, all safety data normally required at the end of the study (i.e. the end-of-treatment visit and long-term follow-up) will be obtained if possible.

4.3.1 Discontinuation of Study Drug

Treatment with study drug may be discontinued for any of the following reasons:

- Progressive disease (as confirmed by central radiographic assessment; see Section [7.2.1](#))
- Adverse event (AE)
- Investigator decision
- Subject decision, Non-AE
- Other

4.3.2 Subject Discontinuation from Study

Any subject may be discontinued from the study for any of the following reasons:

- Subject withdrawal of consent
- Adverse event (AE)
- Death
- Investigator decision
- Lost to follow-up
- Significant noncompliance to protocol
- Study termination by sponsor
- Other

5 TREATMENTS

5.1 Treatments Administered

Rovalpituzumab tesirine, the investigational agent under study in this protocol, is an ADC.

Detailed information describing the preparation, administration, and storage of rovalpituzumab tesirine is located in the Pharmacy Binder.

5.2 Investigational Product

5.2.1 Description

Rovalpituzumab tesirine (SC16LD6.5) drug product is provided in a sterile clear USP Type I 10 mL glass vial [REDACTED] The [REDACTED] drug product is reconstituted with [REDACTED] sterile water for injection [REDACTED]

[REDACTED] The rovalpituzumab tesirine formulation consists of 10 mg/mL rovalpituzumab tesirine in 20 mM histidine hydrochloride, 0.175 M sucrose and 0.4 mg/mL polysorbate 20, pH 6.0. The [REDACTED] drug product is stored and shipped at 2–8°C prior to its use in clinical trials.

A complete description of the chemistry and formulation may be found in the Investigator's Brochure.

5.2.2 Dose and Administration

Dosing is based on subject actual body weight to the nearest tenth of a kilogram, assessed on Day 1 of each cycle, and administered according to the assigned dose.

Subjects must meet all of the following on each dosing day before receiving study drug:

- Absolute neutrophil count (ANC) \geq 1,000/ μ L
- Platelet count \geq 75,000/ μ L
- Clinically-significant AEs occurring during the previous cycle (both clinical and laboratory) have resolved to Grade 0 or 1 (or to baseline grade if preexisting)

Rovalpituzumab tesirine should be diluted into 100 mL normal saline (0.9% NaCl). The infusate should be administered over 30 minutes [REDACTED]

[REDACTED] See the Pharmacy Instructions for details.

5.2.3 Dose Modifications

5.2.3.1 Treatment Delays Due to Toxicity or Progression

Subjects who experience toxicity during a cycle must have recovered as outlined previously in Section 5.2.2 before the next cycle may proceed. If an AE is still ongoing at the time of the next scheduled cycle, the cycle must be delayed until recovery. Specific recommendations are given below.

In the event of isolated CNS progression during study treatment, rovalpituzumab tesirine may be withheld while palliative treatment is administered, e.g., a standard course of whole brain radiotherapy in accordance with institutional practice. During this time, the subject should be fully evaluated for other sites of PD. If progression is isolated to the CNS, study drug may be restarted 1 week after the completion of radiotherapy. If more than 6 weeks have elapsed since the previous dose of study drug, the subject should undergo a radiographic tumor assessment. If additional sites of PD are present, the subject will be required to discontinue study drug, but may be eligible for retreatment.

